5.1.9 Exploratory Efficacy Analysis

5.1.9.1 Analysis of Exploratory Efficacy Endpoints

Exploratory analyses will include:

- Change in Serum Sodium level from baseline at the end of Treatment Phase B compared to the end of Treatment Phase A for nonresponders continuing on tolvaptan therapy
- Quality of life (QoL) assessments
- In all subjects, 24-hour excretion of sodium, creatinine, and osmolality on Days 1 and 2
- 24-hour sodium clearance on Day 1

A paired Student's t-test will be applied to the change from baseline in serum sodium concentration for nonresponders continuing on tolvaptan therapy.

The QoL assessment includes the PedsQL Generic Core Scale (QoL GCS) and PedsQL Multidimensional Fatigue Scale (QoL MFS). For the QoL GCS, the change from baseline in QoL GCS total score, physical health summary score, and psychosocial health summary score will be analyzed by the paired Student's t-test for the responders. For the

QoL MFS, the QoL MFS total score will be analyzed by the paired Student's t-test for the responders.

For the responders, the change from baseline at the end of Treatment Phase A to the end of the Treatment Phase B will be compared between the Early Withdrawal group and the Late Withdrawal group using the same MMRM analysis that is used for the primary endpoint.

Urine osmolality and urine creatinine, potassium, and sodium concentrations will be summarized by collection interval and for zero to 24 hours on Days 1 and 2 in Treatment Phase A using descriptive statistics.

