**3.7.1.2.3 Day 2a (optional)**

The following procedures will be performed on Day 2a for all subjects who are not responsive to tolvaptan treatment at the end of Day 2.

Trough (24 [ $\pm 4$ ] hours post-previous dose)

- 1) Vital signs will be assessed at 24 hours post-previous dose. Blood pressure, heart rate, respiratory rate, and temperature will be assessed after the subject has been supine for  $\geq 3$  minutes. Vital signs should be performed predose and prior to blood draws.
- 2) Clinical status assessments will be performed per inpatient standard of care, eg, subject chart entries will be reviewed (including hyponatremia assessment notes, including laboratory results [trial and nontrial specific], any examination findings,

medical problem list changes, and fluid intake and output) to evaluate the subject's hyponatremia state.

Predose

- 3) A directed physical examination will be performed.
- 4) Body weight will be measured.

Dosing

- 5) Tolvaptan will be administered. If the subject's serum sodium concentration is  $< 135$  mEq/L (mmol/L) and a  $\leq 4$  mEq/L (mmol/L) increase, tolvaptan dose should be adjusted per the titration guidelines ([Section 3.2.4](#)) for the assigned weight group.

Postdose

- 6) A blood sample will be collected for serum sodium testing at 12 ( $\pm 4$ ) hours postdose.
- 7) In addition to serum sodium samples obtained for treatment qualification and efficacy endpoints, supplemental samples for the purposes of safety assessment only can be obtained using a point of care sodium assessment unit, where available, at 6 and 18 hours postdose. A point of care assessment unit is preferred; however, regular blood draws may be used (especially if they can be combined with standard of care labs).
- 8) At the end of the Day 2a visit subjects will be assessed for response to tolvaptan treatment. Subjects who are:
  - a) Responders (serum sodium level increase of  $\geq 4$  mEq/L [mmol/L]) will proceed to Treatment Phase B (see [Section 3.7.1.3](#)) for randomization.
  - b) Nonresponders (serum sodium level increase of  $< 4$  mEq/L [mmol/L]) will continue to Treatment Phase B where they either continue on tolvaptan therapy for 2 additional days or are withdrawn from tolvaptan to be treated per the investigator's preferred standard of care.
- 9) A blood sample will be collected for serum sodium testing at trough (24 [ $\pm 4$ ] hours postdose).

Throughout the visit

- 10) Concomitant medications will be recorded.

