#### **7.4.3 Exploratory Outcome Analyses**

Details will be provided in the statistical analysis plan.

The change in serum sodium concentration in nonresponders continuing on tolvaptan therapy by change from baseline at the end of Treatment Phase B compared to the end of Treatment Phase A will be analyzed using a paired Student's t-test.

The procedure for the analysis of data for the QoL assessments will be provided in the statistical analysis plan (SAP).

The analysis for the following exploratory PD endpoints is described in [Section 6.2](#):

- In all subjects, 24-hour excretion of sodium, creatinine, and osmolality on Days 1 and 2
- 24-hour sodium clearance on Day 1

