5.1.4 Baseline Characteristics and Baseline Comparability

In general, baseline measurements of efficacy and safety variables are defined as their last measurements prior to the first dose of IMP in the corresponding phases.

Demographic characteristics and medical history at Screening will be summarized by descriptive statistics, eg, proportion, mean, median, SD, minimum and maximum values. Use of concomitant medications prior to the start of IMP will be summarized by number and percentage of users by treatment group. These summary statistics will be reviewed to identify any potential lack of balance between the treatment groups.

Baseline characteristics will be summarized for Treatment Phase A and Treatment Phase B, respectively. Baseline characteristics by age categories [REDACTED]

[REDACTED] and by disease etiology [REDACTED]
[REDACTED] will also be provided.

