5.1.7.2 Technical Computational Details for Primary Outcome Analysis

- 1) Baseline for Treatment Phase B is the last evaluation of serum sodium at the end of Treatment Phase A.
- 2) For the Early Withdrawal group, the serum sodium collected at 72 hours post-last dose on the CRF will be used to define the endpoint of Treatment Phase B. For the Late Withdrawal group, the serum sodium collected at 24 hours post-dose (Trough) of Day 4 on the CRF will be used to define the endpoint of Treatment Phase B.
- 3) The MMRM analysis for the primary endpoint will be analyzed using PROC MIXED of SAS (with default REML option). Specifically, the following SAS statements will be used for the primary analysis:

```
proc mixed;
class treatment visit subject agesubgrp responsesubgrp etiologysubgrp;
model change =agesubgrp responsesubgrp etiologysubgrp treatment visit
treatment*visit baseline baseline*visit/ s ddfm=kr;
repeated visit / type=un sub=subject;
lsmeans treatment*visit / pdiff cl alpha=0.05;
run;
```
- 4) In case there is a convergence problem in the MMRM model with the unstructured variance covariance matrix, the following variance covariance matrix structures will be used in the order of 1) heterogeneous toeplitz, 2) heterogeneous autoregressive of order 1, and 3) heterogeneous compound symmetry. The first (co)variance structure which does not have a convergence problem will be the one used for the analysis. If a structured covariance has to be used, the “sandwich” estimator of the variance covariance matrix of the fixed effects parameters will be used in order to deal with possible model misspecification of the covariance matrix.
- 5) Medications for rescue therapy (with indication of hyponatremia) include:
Rescue therapy is defined as any level of fluid restriction, hypertonic saline, isotonic saline (with or without diuretic for purpose of increasing the serum sodium level), plasmapheresis/dialysis, demeclocycline, urea, lithium, commercially available

vaptans, or any treatment intended to raise the level of serum sodium at any time during the trial.

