5.1.9.2 Technical Computational Details for the Analysis of the Exploratory Efficacy Endpoints

- 1) In Treatment Phase A, subjects achieving an increase in serum sodium concentration of ≥ 4 mEq/L (mmol/L) by end of Day 2 (or 2a) will be defined as responders. If subjects do not achieve an increase in serum sodium concentration of ≥ 4 mEq/L (mmol/L) by end of Day 2 (or 2a), they will be defined as nonresponders.
- 2) The QoL GCS scale consists of 23 items encompassing physical, emotional, social, and school domains.

For ease of interpretability, items are reversed scored and linearly transformed to a 0 to 100 scale, so that higher scores indicate better HRQOL (Health-Related Quality of Life).

To reverse score, transform the 0 to 4 scale items to 0 to 100 as follows: 0 = 100, 1 = 75, 2 = 50, 3 = 25, 4 = 0.

To create scale scores, the mean is computed as the sum of the items divided by the number of items answered (this accounts for missing data). If more than 50% of the items in the scale are missing, the scale scores should not be computed. If 50% or more items are completed, then impute missing scores by the mean of the completed items in a scale.

To create the Psychosocial Health Summary Score, the mean is computed as the sum of the items divided by the number of items answered in the Emotional, Social, and School Functioning Scales. The Physical Health Summary Score is the same as the Physical Functioning Scale Score.

To create the total scale score, the mean is computed as the sum of all the items divided by the number of items answered on all the scales.

Child self-reported data for subjects with age ≥ 5 years will be used in the analysis, while for subjects with age < 4 years, parent-reported data will be used.

- 3) The QoL MFS scale consists of 18 items in 3 subscales: general fatigue, sleep/rest fatigue, and cognitive fatigue.

Items are reversed scored and linearly transformed to a 0 to 100 scale as follows: 0 = 100, 1 = 75, 2 = 50, 3 = 25, 4 = 0.

To create scale scores for each dimension, the mean is computed as the sum of the items divided by the number of items answered.

The total QoL MFS score will be calculated by summing up all the items divided by the number of items answered on all the scales.

If more than 50% of the items in the scale are missing, the scale scores should not be computed. If 50% or more items are completed, then impute missing scores by the mean of the completed items in a scale.

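### In nonresponders who stay on tolvaptan, the end-of-Phase-A sodium both classifies the child and is the reference reading, so the exploratory change to the end of Phase B is biased upward

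*SAP*

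**What the plan says.** SAP 5.1.9.1 lists "Change in Serum Sodium level from baseline at the end of Treatment Phase B compared to the end of Treatment Phase A for nonresponders" who continue tolvaptan, and adds: "A paired Student's t-test will be applied to the change from baseline in serum sodium concentration for nonresponders continuing on tolvaptan therapy". Protocol 7.4.3 has the same contrast and test: "The change in serum sodium concentration in nonresponders continuing on tolvaptan therapy by change from baseline at the end of Treatment Phase B", set against the end of Phase A.

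On the reference value, SAP 5.1.7.2 states: "Baseline for Treatment Phase B is the last evaluation of serum sodium at the end of Treatment Phase A". SAP 5.1.4 gives the general rule that baselines are "defined as their last measurements prior to the first dose of IMP in the corresponding phases".

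On classification, SAP 5.1.9.2 says of children whose rise has not reached 4 mEq/L that "they will be defined as nonresponders". SAP 3.1 and Protocol 3.1.1.1 give a child who falls short on Day 2 one more treated day (Day 2a), so a final nonresponder has fallen short twice. Protocol 3.1.1.2 leaves nonresponders unrandomized and lets the investigator decide who continues.

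Two further passages bear on the point. SAP 5.1 says that, given very low enrollment and early termination, the efficacy analyses need not be carried out in the final analysis beyond summary statistics. Protocol Table 3.7.2.1-1 schedules both a 12-hour and a trough sodium on Day 2a, and again on Day 4 for nonresponders who continue. For Day 2a, Section 3.7.1.2.3 reads "A blood sample will be collected for serum sodium testing at 12" (±4) hours postdose.

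**The concern.** A trough sodium is the child's underlying level plus transient fluctuation and assay error. Requiring a low rise at that trough selects children whose fluctuation was negative. Subtracting the same trough from a later reading turns that negative fluctuation into an apparent gain. A paired t-test takes a mean difference of zero as its null, but with no effect of dosing on Days 3 and 4 the expected difference is above zero.

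The stated purpose is to assess efficacy in nonresponders who continue the drug. With no randomized control among them, nothing in the data would separate a real late response from this artefact, and an uncontrolled rise could be read as benefit from continued dosing.

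**Working it through.** **What the plan gives.** It states no sample size, alpha, power or variability for this analysis. The nearest figures are for the primary endpoint: 70 randomized, difference 4, SD 5, 90% power. These reproduce: 4 / (5 × √(2/35)) = 3.35, and 3.35 − 1.96 = 1.39, which is power of about 92% (91.0% with the t distribution). Expected nonresponders are about 100 − 70 = 30, and only those kept on tolvaptan enter the test.

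**Which contrast.** Change from baseline at the end of B compared with that at the end of A is (B − base) − (A − base) = B − A. A pre-dose baseline cancels, leaving the end-of-A trough as reference.

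**Size if one trough did the selecting.** Assume that the observed Phase A rise has SD 5 (borrowed from the primary endpoint), that 30% are nonresponders, and that independent noise has SD s per reading. The noise in the trough, given a rise in the lowest 30%, averages −(s²/5) × φ(z)/0.30, with z = −0.524 and φ(z) = 0.348. The factor is 0.348/0.30 = 1.159. The bias in B − A is therefore 1.159 × s²/5.

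**Size under the plan's two-trough rule.** Failing at both Day 2 and Day 2a roughly halves this. Simulation with no true change, and no real child-to-child spread in Phase B change, gives:

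| s (assumed, mEq/L) | Bias, one trough (formula) | Bias, both troughs | Rejection, n = 15 | Rejection, n = 30 |
|---|---|---|---|---|
| 1 | 0.23 | 0.12 | 6.0% | 7.2% |
| 2 | 0.93 | 0.48 | 9.7% | 15.6% |
| 3 | 2.09 | 1.11 | 17.2% | 31.6% |

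**Allowing real spread.** If the SD of B − A is held at 5, rejection at s = 1, 2, 3 is 5.1%, 6.6%, 13.2% (n = 15) and 5.2%, 8.2%, 23.2% (n = 30). That is 1.0 to 4.6 times 5%.

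**A second set of assumptions.** With a true-response SD of 3, noise SDs of 1 to 3 and 12-hour autocorrelation from 0 to 0.6, the spurious rise is about 0.2 to 1.2 mEq/L. Rejection is about 8% to 41% with no real spread in Phase B change, and 6% to 27% with a real spread of SD 3. The top is 41/5, about 8 times nominal.

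**Does a separate reference reading help?** With independent noise and a reference not used for classification, rejection returns to 4.9% to 5.2% and bias to about 0. The 12-hour Day 2a to 12-hour Day 4 contrast approximates this. With noise SDs of 1.5 to 3 it rejects 4% to 6% of the time at autocorrelation 0, 6% to 12% at 0.3 and 8% to 20% at 0.6. It removes about half of the bias at 0.3, and between a quarter and a third at 0.6.

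**The case against.** The strongest answer is SAP 5.1: in the final analysis no nonresponder t-test is required, so no rejection rate need arise, and the planned 30 or so nonresponders were not reached. The endpoint is also exploratory, sits outside the hierarchical procedure and has no stated alpha. All of that stands, and it makes this a minor point. It does not remove the bias from the mean change, which is the kind of summary that SAP 5.1 keeps.

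A reader might infer a fixed inflation, such as false positives at 2 to 7 times the nominal rate. The documents do not support that. Within-child variability, autocorrelation, the number continuing and the real spread of Phase B change are all unstated. Many reasonable inputs give less than 2 times, and some give more than 7.

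A reader might also infer that the 12-hour contrast cures the problem and should replace the planned one. It does not cure it if fluctuations last beyond 12 hours. It offers no protection if 12-hour values count toward response: in that case, at noise SD 3 with independent fluctuations, its bias is 0.55 mEq/L against 0.56 for trough to trough. The documents leave this open. SAP 5.1.9.2 counts a rise achieved by the end of the day, and Protocol 3.7.1.2.3 lists the response assessment before the trough draw. The 12-hour contrast also asks a slightly different question, since any late effect of the Day 2a dose falls inside it.

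Finally, if the test were applied to the change from the pre-first-dose value alone, the argument would not apply in this form. The comparison with the end of Phase A and the SAP's baseline rules favor the other reading, although SAP 5.1.7.2 sits under the primary analysis.

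**Conclusion.** The point holds as to direction: with the trough as both classifier and reference, the bias was upward in every scenario examined, and nothing in the plan corrects for it. Its size is conditional, and every multiple of nominal quoted here rests on variability figures that are assumed, not taken from the documents. At the upper end, an artefact of about 1 mEq/L is a quarter of the 4 mEq/L that defines response; at the lower end it is negligible. Given SAP 5.1, the likely consequence is a descriptive mean that overstates the gain from continued dosing. An invalid test follows only if the t-test in SAP 5.1.9.1 and Protocol 7.4.3 is run. This is a worthwhile clarification and does not threaten the trial's main conclusions.

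**What to change.** In SAP 5.1.9.1:

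- Keep the protocol-defined end-of-A to end-of-B change in continuing nonresponders, but report it descriptively, with no test of efficacy and a label that it is subject to regression to the mean.
- Beside it, give the mean and 95% CI of the change from the 12-hour post-dose sodium on Day 2a to the 12-hour post-dose sodium on Day 4.
- State that response is classified on the trough reading.
- State the limits of the 12-hour contrast: the ±4 hour window, residual bias if fluctuations outlast 12 hours, and inclusion of any late effect of the Day 2a dose.

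The cost is a few sentences and one extra table row. Both draws are already scheduled, and the protocol's exploratory variable is retained. If only summary tables are produced, the essential part is a footnote on the trough-to-trough mean.

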## 2 Trial Rationale and Objectives

### 2.1 Trial Rationale

The purpose of this trial is to establish the effects of tolvaptan on serum sodium concentration as well as the safety of use of tolvaptan in children and adolescents with euvolemic or hypervolemic hyponatremia secondary to [REDACTED] [REDACTED]. In addition, blood samples will be taken to determine tolvaptan PK specific to a pediatric population, as the absorption, distribution, metabolism, and elimination of drugs in children and adolescents can vary from that of adults. These differences can be due to differences in physiology based on maturity status (eg, GI transit times are faster, the ratio of total body water to body fat is shifting, and the expression of drug metabolizing enzymes change) or based on underlying disease state. Hyponatremia alone does not appear to affect tolvaptan PK; however, tolvaptan exposure is 2-fold greater in adult subjects with CHF compared to healthy adult subjects and clearance appears to decrease about 50% in subjects with moderate to severe hepatic failure (Child-Pugh score > 6). As the primary pharmacodynamic effect of tolvaptan is to produce an increase in urine output (aquaresis), urine output and fluid intake will be determined as PD endpoints.

The proposed population size of 100 subjects is expected to yield 70 subjects who respond to tolvaptan (henceforth termed “responders”), which has adequate power (> 90%) to test for statistical significance in the primary endpoint. Enrollment is expected to take approximately 3 years using approximately 60 sites globally. Additional blood sampling will be included across populations to provide PK information.

Even with a limited size, recruitment for such a trial is expected to be challenging due to the low frequency of AVP-mediated hyponatremia in children. Therefore, the trial will be organized at major pediatric referral centers to access the largest patient population.

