#### **3.5.4      Exploratory Variables**

- Efficacy will be assessed in nonresponders continuing on tolvaptan therapy by change from baseline in serum sodium concentration at the end of Treatment Phase B compared to the end of Treatment Phase A

- In all subjects, 24-hour excretion of sodium, creatinine, and urine osmolality on Days 1 and 2
- 24-hour sodium clearance on Day 1
- Quality of life (QoL) assessments

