### **3.7.1 Schedule of Assessments**

#### **3.7.1.1 Screening**

The procedures listed below will be performed during the Screening Visit (Days –2 to –1) to ensure that the subject qualifies for the trial.

- 1) Trial procedures and information regarding the nature of the trial will be reviewed and written informed consent/assent will be obtained prior to any trial-related procedures.
  - a) Informed consent will be obtained from each subject's parent/legal guardian or legally acceptable representative prior to any trial procedures being conducted.
  - b) Each subject who is able will indicate willingness to participate in the trial by signing or marking an assent form (as applicable) supplied for this purpose.
- 2) Inclusion and exclusion criteria will be reviewed.
- 3) Demographic information will be collected.
- 4) Medical and hyponatremia history will be recorded.
  - a) Medical history should include the subject's current list of medical problems that impacts the subject's current hospital stay.
  - b) The hyponatremia medical history should include the etiology of subject's hyponatremia (see [Section 3.3.1](#)) and what treatment was administered prior to trial enrollment. A detailed history specific to etiology of hyponatremia will also be recorded.
  - c) Any observable symptoms of hyponatremia will be assessed and recorded.
- 5) Vital signs (blood pressure, heart rate, respiratory rate, and temperature) will be assessed after the subject has been supine for  $\geq 3$  minutes. Vital signs should be assessed prior to blood draws.
- 6) A resting 12-lead electrocardiogram (ECG) will be performed after the subject has been supine and at rest  $\geq 10$  minutes.
- 7) Body height and weight will be measured. Growth percentiles will be recorded.
- 8) The initial physical examination should be a full physical. Subsequent physical examinations can be directed physical examinations that are focused on hyponatremia-related signs and symptoms as well as any major changes from baseline.
- 9) Tanner staging will be performed.
- 10) A neurological examination will be performed.
- 11) Quality-of-life (QoL) assessment will be performed, as appropriate by age and where available.
- 12) Clinical status assessments will be performed per inpatient standard of care, eg, subject chart entries will be reviewed (including hyponatremia assessment notes, including laboratory results [trial and nontrial specific], any examination findings,

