**For subjects not receiving tolvaptan treatment (Early Withdrawal group and nonresponders treated with standard of care)**

- 1) Early Withdrawal subjects will be observed to determine whether additional intervention is required to maintain appropriate serum sodium levels.
- 2) Nonresponders discontinuing tolvaptan will continue to be treated per the investigator's preferred standard of care.
- 3) A directed physical examination will be performed.
- 4) A neurological examination will be performed.
- 5) A blood sample will be collected for serum sodium testing at 12 ( $\pm 4$ ) hours post the nominal dosing time.
- 6) A QoL assessment will be conducted.
- 7) Concomitant medications will be recorded.
- 8) Adverse events will be assessed.

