### **3.7.2.3      Quality of Life Assessments**

Two patient-reported outcomes instruments (acute versions with 7 day recall period) will be used to assess subject quality of life: PedsQL Generic Core Scale and PedsQL Multidimensional Fatigue Scale. Both instruments are appropriate for  $\geq 2$  years of age, however availability may be limited for certain ages and languages. The age groups covered by these assessments are Toddler (2–4 years), Young child (5–7 years), Child (8–12 years), and Adolescent (13–18 years). Depending on the subject's age, the questionnaire may be completed by either the subject, subject and parent/caregiver, or the parent/caregiver, as appropriate.

The PedsQL Generic Core Scale consists of 23 items encompassing physical, emotional, social, and school domains.

The PedsQL Multidimensional Fatigue Scale consists of 18 items in 3 subscales: general fatigue, sleep/rest fatigue, and cognitive fatigue. The instrument focuses on the domains of processing speed, attention/vigilance, visual and working memory.

The assessment time points are at screening, Day 4 and 7 days post-last dose.

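### SAP 5.1.9.1 analyses before-after quality-of-life change in sodium responders only, so the uncontrolled result may overstate the change after tolvaptan in treated children

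*SAP*

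**What the plan says.** SAP 5.1.9.1 names the QoL population twice. For the Generic Core Scale (total, physical and psychosocial scores): "psychosocial health summary score will be analyzed by the paired Student's t-test for the responders". For the Fatigue Scale: "QoL MFS, the QoL MFS total score will be analyzed by the paired Student's t-test for the responders". It names no QoL analysis for nonresponders. The following paragraph, also confined to responders, covers change over Phase B, with the end of Phase A as baseline. Its method reads: "will be compared between the Early Withdrawal group and the Late Withdrawal group using the same MMRM analysis that is used for the primary endpoint". It does not say which outcome is meant.

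The protocol sets no such limit. Section 3.5.4 lists "Quality of life (QoL) assessments" without a population, and section 7.4.3 leaves the QoL procedure to the SAP. Collection does not depend on response:

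- Section 3.7.2.3: "The assessment time points are at screening, Day 4 and 7 days post-last dose".
- Section 3.7.1.1 (screening, before response is known): "Quality-of-life (QoL) assessment will be performed, as appropriate by age and where available".
- Section 3.7.1.3.2 (Day 4), under subjects off tolvaptan, which includes nonresponders on standard of care: "A QoL assessment will be conducted". The list for subjects on tolvaptan, which includes continuing nonresponders, has the same item.
- Section 3.7.1.4.2 (7 days post-last dose): collected with no restriction by response.

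SAP 5.1.9.2 defines a responder by a sodium rise of at least 4 mEq/L by the end of Day 2 or 2a. SAP 5.1 opens by stating that, because enrollment was very low and the trial ended early, the final analysis need only give summary statistics for efficacy.

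**The concern.** A paired before-after comparison has no control, so its meaning depends on who is in it. Here membership is decided after dosing, by whether the drug raised sodium. The result describes QoL change in children in whom treatment worked on its main pharmacological measure. It does not describe the children who were given the drug.

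The SAP takes the other route for its key secondary endpoint, which is also an uncontrolled before-after test. SAP 5.1.8.1 runs the sodium change on all subjects in the Phase A Efficacy Sample. The SAP gives no reason for the narrower QoL population. SAP 5.1.1 already defines nonresponder samples, and 5.1.9.1 itself analyses nonresponders' sodium.

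At stake is the reading of an exploratory result. If QoL moves with sodium, the reported mean is higher than the mean in treated children. Nonresponders also complete 23 plus 18 items at up to three visits, and the plan makes no stated use of their answers.

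**Working it through.** **1. The plan's own figures.** The documents give no QoL effect, SD, sample size or correlation with sodium. The 70 is set for the sodium endpoint (SAP 4.1: difference 4, SD 5, two-sided 0.05, 1:1, 90% power). It reproduces: with the noncentral t distribution, power is 0.902 at 34 per arm and 0.910 at 35 per arm. Nothing here affects it. Protocol 2.1 supplies the share needed: "The proposed population size of 100 subjects is expected to yield 70 subjects who respond to tolvaptan". So the responder share is p = 70/100 = 0.70, and 1 - p = 0.30.

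**2. Difference between the two means.** Let dR and dN be the mean QoL change in responders and nonresponders.

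All-treated mean = p·dR + (1 - p)·dN

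Responder mean minus all-treated mean = dR - p·dR - (1 - p)·dN = (1 - p)(dR - dN) = 0.30 (dR - dN)

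**3. Ratio.** Let r = dN/dR, with dR > 0. Then responder mean / all-treated mean = 1/(0.70 + 0.30r).

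| Assumed r | Calculation | Ratio |
|---|---|---|
| 0 (nonresponders gain nothing) | 1/0.70 | 1.43 |
| 0.5 (half the gain) | 1/0.85 | 1.18 |
| 1 (equal gain) | 1/1.00 | 1.00 |
| 1.5 (larger gain) | 1/1.15 | 0.87 |

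**4. Other responder shares.** With r = 0 the ratio is 1/p: 1/0.6 = 1.67 for p = 0.6 and 1/0.9 = 1.11 for p = 0.9 (both shares assumed).

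**5. The same question in SD units.** Treat responders as the top 70% of a normal distribution of sodium change. Their mean sodium change then lies φ(z)/p = 0.497 SD above the mean of all subjects. If QoL change correlates with sodium change at ρ, the responder QoL mean is shifted by 0.497ρ SD. For assumed ρ of 0, 0.2, 0.4 and 0.6 the shift is 0.00, 0.10, 0.20 and 0.30 SD of QoL change.

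**6. Who is on drug at the QoL visits.** Early Withdrawal responders, about half of responders under 1:1 allocation, get no tolvaptan on Days 3 and 4, so they are off drug at the Day 4 assessment. At 7 days post-last dose everyone is off trial drug. The instruments use a 7-day recall, so Day 4 answers also reach back before the first dose.

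**7. The Early versus Late comparison.** Its stated baseline is the end of Phase A. QoL is scheduled at screening, Day 4 and 7 days post-last dose, with nothing at the end of Phase A. If this comparison is meant for QoL, it cannot be run as written.

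**The case against.** The strongest reply is that SAP 5.1 has withdrawn the obligation to run these tests, so there is little left to correct. That stands for the t-tests. Summary statistics remain, though, and responders are still the only QoL population that 5.1.9.1 names. The open question is whom the summary covers.

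A second reply is that the protocol and SAP do not conflict. Protocol 3.5.4 sets no analysis population, the SAP was asked to supply the procedure, and it labels its population openly. In a randomized-withdrawal design it is also natural to follow the responders. All of this is fair. The point is therefore about an unhelpful choice of population and should not be read as a contradiction between the documents.

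A reader might infer that the responder restriction does overstate the QoL gain on tolvaptan. The documents do not support that. The sign depends on dR - dN, about which they say nothing. Nonresponders could improve as much or more, since some move to the investigator's standard of care. The words on tolvaptan would also be wrong for Early Withdrawal children at Day 4.

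A reader might also infer that 30% of QoL data are discarded. The 30% is a planning figure for all treated children. PedsQL applies from age 2 and may be unavailable for some ages and languages, while the trial admits infants from 4 weeks. The nonresponder share among children who can be assessed is unknown, and early termination has overtaken the planned numbers.

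Finally, an all-dosed mean is still uncontrolled and mixes four treatment courses. That is correct, and it is why rows by group and an explicit label are needed beside it.

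**Conclusion.** The concern holds in a limited form. SAP 5.1.9.1 confines before-after PedsQL change to a group selected on a post-dose outcome, although the same scores are collected in nonresponders of suitable age. The uncontrolled result may overstate the QoL change after tolvaptan in treated children.

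On the planned 70% yield, the ratio of responder mean to all-treated mean runs from 1.00 with equal changes to 1.43 if nonresponders gain nothing, and falls below 1 if they gain more. Both the direction and the size rest on assumed nonresponder changes. The responder share is itself a planning figure.

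The weight is minor. QoL is exploratory, so no type I error, power or confirmatory claim depends on it. It is still worth correcting: very low enrollment makes each treated child with scores more valuable, and the data are already scheduled for collection.

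**What to change.** In SAP 5.1.9.1, replace the responder-only QoL population with a descriptive summary of change in both PedsQL scales, from screening to Day 4 and from screening to 7 days post-last dose:

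- one row for all dosed subjects with both scores;
- separate rows for responders in the Early and Late Withdrawal arms;
- a row for nonresponders;
- a label stating that the before-after changes are uncontrolled.

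State whether the Early versus Late paragraph applies to QoL. If it does, name screening as the QoL baseline, because none is scheduled at the end of Phase A.

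The cost is a wording change and a few extra table rows, with no new data. The exploratory QoL figure may come out less favourable.
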